### **3.4 Primary Endpoints**

- A. The number of patients with a high-grade glioma who achieve a > 50% reduction in focal seizures with PER 4 mg daily after failing 1 or more ASDs at 3 and 6 months.
  1. The overall survival of patients with high-grade glioma treated with PER at 3 months.
  2. Decline in neuropsychological function at 6 months.

All comparisons will use intent to treat model for patients initiated or exiting PER therapy. In event of patients not surviving till 12 months, most recent data prior to death will be used for correlation.

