- EEG will be obtained at baseline and at 3 months and 12 months to identify changes in background activity (e.g. diffuse slowing) and epileptiform discharges to correlate with focal seizure presence vs absence.
- Neuropsychological batteries will be obtained at baseline, 3 months, and 6 months to determine the presence or absence of significant neurocognitive decline.

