### **6.7 Visit 7**

Visit 7 will be completed by telephone call. Seizure frequency is assessed. Seizure Diary is reviewed. PHQ-9, NDDI-E, CGIC, C-SSRS and QOLIE-31 are completed by asking the participant the questions verbally. The participant will be asked about medical history.

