#### Handling of Missing Data

Study data will be collected and managed using REDCap electronic data capture tools hosted at Mayo Clinic. All data requested on the Case Report Form (CRF) will be recorded for each participant. A standardized CRF will be generated by REDCap. For any data query, the Principal Investigator and Investigators will meet to clarify the data queried and make corrections based on consensus. Once the study is completed, the Principal Investigator will randomly select 3 participants and compare the data documented for each on the CRF with what is entered into the REDCap database. If there is any discrepancy, the Principal Investigator and/or Investigators will cross-reference all 20 patients to ensure accuracy.

**Primary Hypothesis:** We hypothesize that perampanel will lead to a significant reduction in seizure frequency for adult patients with brain tumor-related seizures associated with high-grade glioma.

We will compare seizure frequency before and 3 months after treatment with monotherapy and adjunctive PER and use descriptive statistics to demonstrate differences in responders. A P-value < 0.05 will be used to reflect statistical significance.

**Secondary Hypothesis 1:** We hypothesize the progression of brain tumor (comparing 4 and 8 mg/d of perampanel) based upon fusion by comparing baseline brain MRI and MRI at 12 months will be less for IDH-mutants.

We hypothesize there will be minimal or no change in neurocognitive function from 0 to 3 months on Montreal Outcome Cognitive Assessment (MOCA; higher scores indicating greater function); and the Clinical Global Impression of Change (CGIC; scores from 1 to 7, with lower scores indicating greater improvement and a score of 4 indicating no change).

Chi-square and Student T-test will be used to measure differences in assessment and change during the study period. A P-value < 0.05 will be considered significant.

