### Assessment 5: Clinician's Global Impression of Change

**TABLE 2. CGI-I guidelines**

1	= Very much improved—nearly all better; good level of functioning; minimal symptoms; represents a very substantial change
2	= Much improved—notably better with significant reduction of symptoms; increase in the level of functioning but some symptoms remain
3	= Minimally improved—slightly better with little or no clinically meaningful reduction of symptoms. Represents very little change in basic clinical status, level of care, or functional capacity
4	= No change—symptoms remain essentially unchanged
5	= Minimally worse—slightly worse but may not be clinically meaningful; may represent very little change in basic clinical status or functional capacity
6	= Much worse—clinically significant increase in symptoms and diminished functioning
7	= Very much worse—severe exacerbation of symptoms and loss of functioning

Adapted from Spearing MK, Post RM, Leverich GS, et al. Modification of the Clinical Global Impressions (CGI) Scale for use in bipolar illness (BP). *Psychiatry Res* 1997;73(3):159–71.

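### The 6-month neuropsychological endpoint has no matching analysis: the only cognition hypothesis stops at 3 months and rests partly on CGIC, a global rating

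*Combined protocol and SAP*

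**What the plan says.** Section 3.4 (Primary Endpoints) lists "Decline in neuropsychological function at 6 months". It gives no instrument, threshold or comparison. Section 2 places neurocognition among the secondary objectives and asks for a comparison with alternate ASDs.

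Section 3.5 explains what the data are for: "Neuropsychological batteries will be obtained at baseline, 3 months, and 6 months to determine the presence or absence of significant neurocognitive decline". The tests in the batteries are not named. The Schedule of Events and sections 6.2, 6.8, 6.11 and 6.15 place the neuropsychology assessment at baseline and Days 90, 180 and 300. MOCA and CGIC are also completed at Day 180 (section 6.11).

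The analysis is in section 7.2, under Secondary Hypothesis 1 (printed below the Handling of Missing Data subheading): "We hypothesize there will be minimal or no change in neurocognitive function from 0 to 3 months on Montreal Outcome Cognitive Assessment". The same sentence adds CGIC, described as "scores from 1 to 7, with lower scores indicating greater improvement and a score of 4 indicating no change". The method is one sentence: "Chi-square and Student T-test will be used to measure differences in assessment and change during the study period", at a 0.05 level.

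Assessment 5 in the Appendix gives the CGIC levels. The middle level reads "No change—symptoms remain essentially unchanged".

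**The concern.** An endpoint needs a named measure, a time point and a comparison. Here the endpoint is at 6 months, while the only stated hypothesis is at 3 months and uses two other instruments. If the plan is followed as written, the trial could report on cognition from Day 90 MOCA and CGIC, and the Day 180 assessment could be collected without a prespecified use.

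CGIC adds a second problem. The trial hypothesises that PER reduces seizures. A rating that rises and falls with overall symptoms may improve because seizures improve, and reading it as cognition would mix two outcomes that the study wants to separate.

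**Working it through.** The plan states no power, effect size or SD for neurocognition, so there is no figure to reproduce. The check sets the passages side by side and adds one illustration.

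**1. Endpoint against analysis**

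| Item | Endpoint (3.4, 3.5, Schedule) | Named hypothesis (7.2) |
|---|---|---|
| Time point | 6 months (Day 180) | 0 to 3 months (Day 90) |
| Instrument | Neuropsychological battery, tests not named | MOCA and CGIC |
| Direction | Decline, not defined | Little or no change, no margin |
| Comparison | Not stated in 3.4; section 2 says with alternate ASDs | Not stated |

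The follow-up analysed is 90/180 = half of that in the endpoint.

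**2. What CGIC measures.** The seven levels in Assessment 5 refer to symptoms, functioning and, at one level, level of care. None names cognition, and none tells the rater to set seizure change aside. Take a patient whose seizures fall while cognition worsens. Level 2 asks for better functioning, level 3 describes little or no meaningful symptom reduction, and levels 5 to 7 describe worsening. No level fits cleanly, so the rater must net the two changes and the score cannot be split afterwards. That is enough to disqualify it as a cognitive measure.

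**3. CGIC at baseline.** Section 6.2 and the Schedule have CGIC completed at baseline. It is already a rating of change, so a baseline value has no clear meaning, and neither does a change in it from 0 to 3 months.

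**4. What a non-significant test would show (illustration only).**
- Inputs from the plan: 10 per group (section 4.3) and alpha 0.05 (section 7.2).
- Assumptions: two-sided test; all 20 patients observed; a between-group difference of d SD at month 6 that builds up linearly, so d/2 at month 3.
- Formula: power = P(|T| > t), where T is noncentral t with 2 × 10 − 2 = 18 df and noncentrality d × √(10/2).
- For d = 1.0, the noncentrality is 2.236 at month 6 and 1.118 at month 3.

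| d at month 6 (SD) | Power at month 6 | Power at month 3 |
|---|---|---|
| 0.5 | 0.185 | 0.083 |
| 0.8 | 0.395 | 0.135 |
| 1.0 | 0.562 | 0.185 |
| 1.5 | 0.887 | 0.355 |

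The difference detectable with 80% power is about 1.32 SD. The 95% interval for a difference has half-width of about 2.101 × √(2/10) = 0.94 SD. A non-significant result at either time point therefore cannot support little or no change, and one at month 3 says less still about month 6.

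**5. Two secondary checks.**
- Phone visits: sections 6.7, 6.9, 6.10 and 6.12 to 6.14 list CGIC ("CGIC, C-SSRS and QOLIE-31 are completed by asking the participant the questions verbally"), while the Schedule of Events appears to show none at those visits. Baseline and Day 90 are not phone visits, so the 0 to 3 month comparison is not affected.
- MOCA repetition: Visits 2, 3, 4, 5, 6 and 8 (baseline and Days 7, 14, 21, 30 and 90) make six administrations by Day 90. The Appendix shows one form, with one five-word recall list worth 5 of 30 points. A practice gain in the within-patient change is possible. Its size is not in the documents; if it were 1 to 2 points (assumption), it would offset a true loss of 1 to 2 points.

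**The case against.** The strongest reply is that month 6 is not shut out. The method sentence in section 7.2 covers the whole study period, section 7.3 speaks of evaluability at 3, 6 and 12 months, and all three assessments are made at Day 180. This stands against any claim that the plan forbids a 6-month analysis. It does not supply one: neither section names an instrument for month 6 or says what counts as decline.

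A second reply is that this is a 20-patient feasibility pilot, declared unpowered in section 7.1, with neurocognition as a secondary objective. That limits the weight of the point. Section 7.2 still applies a 0.05 test to this hypothesis, and a pilot for a larger trial needs a usable endpoint definition.

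A reader might also infer several stronger things that the documents do not support:
- That every flaw pushes towards finding no decline. No direction can be shown for the baseline or phone CGIC.
- That the phone visits turn CGIC into self-report. The text says that the questions are put to the participant, not that the participant assigns the rating.
- That better seizure control masks decline on MOCA. MOCA tests cognition directly, so the argument applies to CGIC alone.
- That practice gain invalidates MOCA. One specimen form does not show that alternate forms will not be used, and both groups follow the same MOCA schedule, so a gain would largely cancel between them.

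**Conclusion.** The point holds in a limited form and should be corrected. The 6-month endpoint has data collection behind it but no matching analysis and no definition of decline, and the one cognition hypothesis stops at half that follow-up. CGIC should not serve as evidence on cognition; this is inferred from its anchors, not stated in the documents. Its baseline completion has no clear meaning.

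The mismatch itself rests on no numerical assumption. The power figures depend on the assumed linear build-up and full follow-up, and serve only to show that a non-significant test is weak evidence of stability. The MOCA practice effect is possible but unquantified. The phone-visit discrepancy is a matter for reconciliation only.

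**What to change.** In section 7.2:
- Make the neurocognition analysis the change from baseline to Day 180 on the scheduled neuropsychology assessment, compared between groups and reported as an estimate with a confidence interval. First name its tests and score, and fix the threshold for decline in advance.
- Report MOCA at Day 90 and Day 180 as supportive. State that a non-significant test will not be read as no change.
- State how the section 3.4 rule on patients who die (use of their latest data before death) applies here. Applied to this endpoint, it would carry earlier scores into the month-6 result.
- Take CGIC out of the neurocognition hypothesis, report it as a global rating only, and drop the baseline rating.

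Elsewhere, reconcile the phone-visit sections with the Schedule of Events on CGIC, and consider alternate MOCA forms to reduce practice gain.

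Cost: no new visits or assessments. The work is more than wording, because the battery's tests and threshold must be chosen first. The result comes at 6 rather than 3 months, with more loss to death or dropout.

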### **3.5 Identification of Source Data**

Electronic medical records will be maintained via a RedCAP database for consecutive and prospective collection of data.

Efficacy measures used in the study include: clinical assessments will include serial brain MRI, EEG, anti-seizure drug levels and subject self-assessment at clinical follow-up; Neurological Disorders Depression Inventory for Epilepsy (NDDI-E), assessment for screening of depression PHQ-9;Montreal Outcome Cognitive Assessment (MOCA); Clinical Global Impression of Change (CGIC) score; Columbia –Suicide Severity Rating Scale. Seizure calendars performed at 2 months prior to initiation of therapy or adequate reliable historical baseline, and then monthly during study; and QOLIE-31, (see schedule of events for frequency of assessment).

Anatomic brain MRI with perfusion scanning/gadolinium will be obtained at 3 months and then every 3 months, to examine the correlated progression of brain tumor, or the absence of tumor. Laboratory studies will be employed before and after PER initiation. EEG will be obtained at baseline and at 3 months and 12 months to identify changes in background activity (e.g. diffuse slowing) and epileptiform discharges to correlate with focal seizure presence vs absence. Neuropsychological batteries will determine the presence or absence of significant anxiety, depression or cognitive changes over time and quality of life inventory will be obtained at the beginning, intermediate and end of the trial.

The following source data will be directly recorded on the Case Report Form (CRF):

- A comprehensive History and Physical examination and Neurological examination will occur at the initial screening/baseline.
- Clinical visitation will occur at screening/baseline, 3, 6, and 12 months.

Survey questionnaires will be obtained at baseline, 3, 6, 9, and 12 months. The following source data will not be directly collected in the Case Report Form (CRF), but will be captured in supportive documentation (study source documents, EMR):

- Laboratory studies will be employed at baseline and at each clinical visit after PER initiation.
- Brain tumor tissue will be assessed for the usual molecular markers (i.e., IDH-mutant vs wildtype, MGMT methylation, ARX).
- 12-lead ECG will be obtained at baseline and as clinically indicated
- Anatomic brain MRI with and without gadolinium will be obtained at baseline and follow-up brain MRI at 3 months and 6 months during PER use.
- EEG will be obtained at baseline and at 3 months and 12 months to identify changes in background activity (e.g. diffuse slowing) and epileptiform discharges to correlate with focal seizure presence vs absence.
- Neuropsychological batteries will be obtained at baseline, 3 months, and 6 months to determine the presence or absence of significant neurocognitive decline.

## 4 Subject Selection Enrollment and Withdrawal

### 4.1 Inclusion Criteria

1. The subject, or the subject's legally acceptable representative is willing to participate in a clinical trial, provides written informed consent, and subject provides written assent, as required by the Mayo Clinic Institutional Review Board (IRB) policy involving human subjects. In the event of subject lacking the capacity or losing the ability to consent, consent will be deferred to subject's legally acceptable representative
2. Subjects that meet the following diagnostic criteria:
  - a. Patients with established clinical diagnoses of biopsy-proven high-grade glioma (Grade II or above) and epilepsy refractory to at least 1, drug with a seizure frequency of at least 1 seizure episode per 3-months prior to baseline visit.
3. Subjects with body weight of  $\geq 40$  kg and  $\leq 125$  kg at screening.
4. Adults age 18 and older.

### 4.2 Exclusion Criteria

1. Subject has serious cardiac, respiratory, renal, gastrointestinal, hematologic, or other medical condition as determined by the investigator to potentially interfere with the study
2. Subjects with glioblastoma not following Stupp protocol for treatment of glioblastoma.
3. History of status epilepticus in the 6 months prior to screening or a history of seizure clusters progressing to status epilepticus.
4. Past medical history of drug and/or alcohol abuse
5. Pregnant or breast-feeding
6. Subjects treated with PER prior to baseline
7. Prior felony conviction disclosed by the patient or previously stated in medical record.
8. History of violent behavior
9. Clinically significant laboratory abnormality at screening or baseline visits, as determined by the investigators
10. Use of an investigational drug or device within 20 days prior to treatment Day 1
11. Repeated radiation therapy for tumor regrowth
12. Subjects that plan to undergo tumor resection on or after baseline visit
13. Uncontrolled psychiatric disorder at baseline

14. Subjects who report active suicidal attempts or suicidality including subjects with a history of suicide attempts or suicidality determined to be clinically significant by investigators at screening.

#### **4.3 Subject Recruitment, Enrollment and Screening**

Subjects (n = 20), will be male and female adults with a high-grade glioma recruited from Mayo Clinic in Jacksonville, Florida- [name], DO, (PI). 10 subjects will be enrolled into an adjunctive Perampanel and other ASDs group, and 10 subjects will receive only alternative ASDs. There will be a 6-month recruitment period for screening and enrollment. The treating physician will decide, based on best medical practice, which patients are candidates for adjunctive Perampanel and other ASDs, or only alternative ASDs. Patients taking Perampanel will begin their titration phase upon enrollment.

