Study Product, Dose, Route, Regimen	PER is a noncompetitive AMPA glutamate receptor antagonist. The two phases of the treatment portion of this study include a titration phase and a stable dosing phase. This study will have two treatment arms consisting of PER and alternative ASD arm. The PER arm will begin a titration phase with 2mg PER PO q.d. (may be split to b.i.d.) for one week and increase by 2mg/week until reaching an initial dose of 4mg PO q.d. (q.d. or b.i.d. dosing) is reached. Flexible dosing of PER above 4mg to a maximum of 8 mg daily will be compared to use of alternative ASDs and be guided by best clinical practices with dosing and indication within U.S. FDA guidelines.
Duration of Administration	Participants will be assigned to receive open label PER or an alternate ASD for at least 12 week and up to 40weeks for the remainder of the study. This includes 2-4 weeks of titration and up to 40 weeks of stable dosing. Reduction by 2 mg will be allowed in cases of efficacy if doses greater than 4 mg daily result in non-idiopathic side-effects.
Reference therapy	All comparisons will use standard ASDs as the reference therapy using an intent to treat study design for patients initiating or tapering off PER therapy.
Statistical Methodology	Statistical analysis will include Student T-test, Chi-square for categorical differences. An interim analysis will be performed when half of the targeted subjects are enrolled.

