## 2 Study Objectives

### Primary Objective

Demonstrate the efficacy and safety of PER on seizure frequency in adult patients with biopsy-proven high-grade glioma and focal Epilepsy compared with alternate ASDs.

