### 5.3 Method for Assigning Subjects to Treatment Groups

Participants will be assigned to receive:

Group A: open label arm of adjunctive PER (study drug) for patients with seizures treated with at least 1 ASD administered in escalating divided doses of 2 mg/week to 4 mg daily with flexible dosing to 8 mg/day by 4 weeks. Subjects must undergo forced titration of 2 mg/week and be able to tolerate 4 mg to continue in the study. Concomitant ASD will be utilized according to best clinical practice.

or

Group B: continued open label treatment for patients with seizures treated with at least 1 ASD, as per best medical practice, without the use of PER.

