### 7.2 Statistical Methods

#### Descriptive Statistics

Statistical analysis will include Student T-test, Chi-square for categorical differences. An interim analysis will be performed when half of subjects are enrolled.

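### The treating physician chooses who gets perampanel, so the comparison with alternate ASDs can be estimated but not demonstrated, and should be worded and analysed as non-randomised

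*Combined protocol and SAP*

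**What the plan says.** **Allocation.** Section 4.3 fixes the group sizes and says who assigns: "10 subjects will be enrolled into an adjunctive Perampanel and other ASDs group, and 10 subjects will receive only alternative ASDs", and then "The treating physician will decide, based on best medical practice, which patients are candidates for adjunctive Perampanel and other ASDs, or only alternative ASDs". Section 5.3, despite its heading on assignment method, only describes the two groups. Group B is "continued open label treatment for patients with seizures treated with at least 1 ASD, as per best medical practice, without the use of PER". Section 5.8 confirms that the study is open label.

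**Objective.** Section 2 reads: "Demonstrate the efficacy and safety of PER on seizure frequency in adult patients with biopsy-proven high-grade glioma and focal Epilepsy compared with alternate ASDs". The Study Summary gives the same objective with the verb *evaluate*, and Section 3.1 also speaks of *evaluating*. On the comparator the Study Summary is firm: "All comparisons will use standard ASDs as the reference therapy".

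**Analysis.** Section 7.2 opens with "Statistical analysis will include Student T-test, Chi-square for categorical differences". Under the primary hypothesis it adds "We will compare seizure frequency before and 3 months after treatment with monotherapy and adjunctive PER and use descriptive statistics to demonstrate differences in responders", with significance at P < 0.05. The two tests are named again after the secondary hypothesis, for differences in assessments and change. Section 7.1 says that the 20 patients form a feasibility pilot and that the study is not powered for effectiveness.

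The documents contain no randomisation, stratification, matching, covariate adjustment or baseline-balance check, and no statement that the groups may differ for reasons other than treatment.

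**The concern.** The objective is comparative and causal, but the arms are formed by clinical judgement about each patient. Whatever leads a physician to add PER for one patient and not for another may also bear on seizures, cognition, progression or survival. A plain t-test or chi-square attributes the whole of the resulting difference to the drug.

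The bias could favour either arm, because physicians might reserve PER for harder cases or offer it to fitter patients. A reader of the results therefore could not mentally correct for it. The stakes go beyond this study, since the pilot is meant to inform a larger multi-center trial and a selected contrast would be carried into that trial's assumptions.

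**Working it through.** There is no stated figure to reproduce: the plan gives no effect size, response rate, standard deviation or power. The check is a comparison of sections, followed by an illustration.

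**1. Do the sections fit together?**
- Section 4.3: the arm is chosen by the physician.
- Section 2 and Study Summary: the claim is relative to alternate ASDs, with standard ASDs as reference throughout.
- Section 7.2: only two-group or simple change tests are named, without covariates.

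The first makes the arms non-comparable by design, the second needs them to be comparable, and the third does nothing to close the gap.

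**2. How large could the bias be?** All inputs in this step are assumptions. Take one binary prognostic factor and no drug effect. Then

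bias = (difference between arms in the share with poor prognosis) × (difference in response rate between good and poor prognosis).

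*Example:* 40% versus 70% poor prognosis; response 50% if good and 20% if poor.
- Arm with 40% poor: 0.60 × 0.50 + 0.40 × 0.20 = 0.38
- Arm with 70% poor: 0.30 × 0.50 + 0.70 × 0.20 = 0.29
- Spurious difference: 0.38 − 0.29 = 0.09, which equals 0.30 × 0.30

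*Range:* imbalances of 10 to 50 points and prognostic effects of 20 to 40 points give 0.10 × 0.20 = 0.02 up to 0.50 × 0.40 = 0.20.

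**3. How does that compare with chance error at 10 per arm?** The pooled rate in the example is (0.38 + 0.29)/2 = 0.335. The standard error of the difference is √(2 × 0.335 × 0.665 / 10) = √0.0446 ≈ 0.21. The 9-point bias is 0.9 of a patient out of 10 and less than half of one standard error.

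**4. How often would it produce P < 0.05?** This enumerates every 10 v 10 outcome exactly, using the uncorrected chi-square, two-sided (the plan does not state sidedness), with no drug effect and response of 50% v 20% by prognosis.

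| Good-prognosis share, arm v arm | Spurious difference | Chance of P < 0.05 |
|---|---|---|
| 50% v 50% | 0 points | 3.9% |
| 60% v 40% | 6 points | 4.6% |
| 70% v 30% | 12 points | 6.9% |
| 90% v 10% | 24 points | 17.1% |

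The last row is an 80-point imbalance, beyond the range in step 2.

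**5. Would more patients help?** No. In the 70% v 30% case (41% v 29% responding, no drug effect), the power formula at 100 per arm gives P < 0.05 about 43% of the time. A larger sample makes the bias easier to mistake for an effect.

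**The case against.** - **It is a declared pilot.** Section 7.1 disclaims power for effectiveness. That is an honest statement about precision and it lowers the stakes, but bias is a separate matter. The plan also keeps *Demonstrate*, a hypothesis of significant reduction and a 0.05 threshold.

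- **The between-group test may not be the primary analysis.** A reader might infer that it is settled as such. The documents do not support that: Section 7.2 words the primary analysis as before versus after with descriptive statistics, and the Section 3.4 endpoint counts responders on PER. The plan leaves open whether the inference is within or between groups. However, the within-group reading does not meet the comparative objective, and it is itself open to regression to the mean and to concurrent tumour treatment.

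- **Baseline is not ignored.** A reader might conclude that nothing is adjusted for. In fact a reduction of more than 50% is measured against each patient's own baseline. This does not make the arms comparable: if patients were picked for PER after a bad spell, they would tend to improve anyway.

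- **The selection factors are not stated.** It is tempting to say that physicians will select on grade, seizure burden or psychiatric risk. Section 4.3 says only best medical practice. Prior ASD exposure (Sections 1.5 and 5.2) guides the choice of the other ASD, not of the arm, and the Section 4.2 exclusions narrow psychiatric risk in both arms. The mechanism is plausible, but its drivers and direction are unknown.

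- **Imprecision dominates at this size.** This stands. Step 4 shows little excess of false significance unless the imbalance is extreme.

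**Conclusion.** The concern holds in this form: allocation is by physician's choice, the objective is comparative, and no between-group adjustment is planned, so a difference between the arms cannot be read as a drug effect. The conclusion rests on the text and needs no assumed number.

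The size does rest on assumptions. The 9 points, the range of 2 to 20 and the percentages in the table all come from chosen response rates and imbalances, and none is evidence of what will happen in this study. With 10 per arm the practical harm is an over-read estimate more than frequent false significance.

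A reader might go further and infer that the study must be randomised now. The documents do not support that as a simple repair: it would be a different study, at one site with a 6-month recruitment window, and limiting it to patients suited to either option would shrink the pool. Randomisation is a consideration for the later multi-center trial.

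**What to change.** 1. **Claim.** Reword the primary objective in Section 2 as estimating the effect in a non-randomised comparison, and bring the Study Summary into line. In Section 7.2, report between-group differences as estimates with confidence intervals, not as a P < 0.05 demonstration of efficacy.
2. **Adjustment.** Analyse between-group seizure rate and MoCA with arm and the baseline value of that outcome as the only terms. One covariate is a sensible limit at 10 per arm. Both baselines are already collected at Visit 2 (Section 6.2). The seizure baseline needs a single window, since Sections 3.1 and 3.5 use two months and the Section 4.1 entry criterion uses three. State in the plan that baseline adjustment does not remove confounding by indication.
3. **Transparency.** Tabulate WHO grade, IDH status and number of prior ASDs by arm, and add one field for the physician's reason for choosing the arm. Tumour markers (Section 3.5), medical history and concomitant medications (Schedule of Events) are already recorded.

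**Cost:** plan text, one data field and slightly more analysis, with no extra visits or patients. The price is a weaker claim. The documents do not say how far enrolment has gone; for patients already assigned, the reason would have to be taken from the chart. This is a cheap improvement and should be made.
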